For Aim 2 we will plot daily diary ratings of pain intensity expressed as percentage change from baseline pain intensity (mean intensity over the 7 days of baseline). The point where the mean change for the whole sample achieves 30% (“moderately clinically meaningful effect” p.239, [137]) will reveal a potential candidate for an optimal treatment dose. We will also examine pain sensitivity (ischemia, heat) changes over the 4 lab visits. Hypothesis 3: We expect (i) a $\geq 30\%$ reduction in pain intensity ratings and (ii) a $\geq 30\%$ reduction in pain sensitivity (ischemia and thermal pain) by the 13th day of morning bright light treatment. As a preliminary analysis, we will examine these data with a within-subjects ANOVA to determine: a) effect size of change over 13 days of treatment; b) statistical significance of this change; c) whether there is significant non-linearity indicating that response to treatment reached a plateau. In an effort to understand a plateau effect, we will use a piecewise linear mixed model with a fixed change point occurring at the 30% change level. Random effects for time before the change point and time after change point will be included in the model. We will use graphical analyses to investigate violations of the model assumption. Secondary analyses for daily ratings of mood and sleep will be conducted similarly. For additional secondary analyses involving PTSD, depressive and anxiety symptoms, and sleep questionnaires, we will subject data to within-subjects ANOVAs to determine: a) effect sizes of changes over 13 days of treatment; b) statistical significance of these changes; c) whether there is significant non-linearity indicating that treatment response plateaued.

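### The Aim 2 plateau model puts its change point at the 30% clinical threshold, so it describes change after 30% rather than the plateau, and it cannot be fitted if 30% is not reached before day 13

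*SAP*

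**What the plan says.** In the SAP, Data Analysis, Aim 2, daily pain ratings are expressed as percentage change from the 7-day baseline mean. The 30% level first appears as a clinical-importance threshold taken from a cited source: "The point where the mean change for the whole sample achieves 30"% is to suggest a candidate treatment dose. Hypothesis 3 expects a reduction of at least 30% "by the 13th day of morning bright light treatment". A within-subjects ANOVA then examines, among other things, "whether there is significant non-linearity indicating that response to treatment reached a plateau".

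The piecewise model follows. Its purpose is given as "In an effort to understand a plateau effect", and its form as "we will use a piecewise linear mixed model with a fixed change point occurring at the 30% change level". The plan adds: "Random effects for time before the change point and time after change point will be included in the model". Model checking is covered by one sentence: "We will use graphical analyses to investigate violations of the model assumption". For other diary outcomes the plan says: "Secondary analyses for daily ratings of mood and sleep will be conducted similarly".

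The plan does not provide for estimating the change point or comparing alternatives. It gives no rule for a sample whose mean does not reach 30%. It also does not say whether the 30% level is the sample mean's or each subject's. I read it as the sample mean's, by analogy with the dose candidate; this is an inference.

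**The concern.** A two-slope model describes a plateau through its second slope, and that slope describes the flat phase only if the knot sits where the curve flattens. Here the knot is tied to a level of clinical importance, which has no necessary link to the shape of the response. Hypothesis 3 treats 30% as a floor, so levelling off above 30% fits the plan's own expectation. In that case the second slope would show pain still falling although response has already flattened. Hypothesis 3 also allows the crossing to come as late as the last treatment day, and as a hypothesis it may fail. Either event leaves the model without a usable second segment. What is at stake is a pilot's statement about whether and when response levels off, which could inform treatment duration in later work.

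**Working it through.** The plan gives no figure for this model, so there is none to reproduce. The check asks what the stated rule returns for known curves.

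**Inputs from the documents.** There are 13 treatment days (6 plus a further 7 in the Protocol; day 13 in Hypothesis 3), the knot is at 30% change, and n = 30 (SAP, Aim 1).

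**Assumptions.** The mean curve falls in a straight line to a reduction of p% on day b and is flat afterwards. The documents give no SDs, so four sets were used (between-subject / day-to-day / slope, in points and points per day): 10/15/1.0, 15/25/1.5, 25/25/1.5 and 20/35/2.0. Daily errors are independent and diaries complete.

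**Step 1: the knot without noise.** On the straight segment the mean reaches 30% on day k = 30 × b / p. The model fitted by least squares over days 1-13 is y(d) = a + β1·min(d, k) + β2·max(d − k, 0). The true slope after the bend is 0.

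| Curve | k | β2 (points/day) | Fall still to come after 30% |
|---|---|---|---|
| 30% from day 6, 7 or 10 | 6, 7 or 10 | 0 | 0 |
| 35% from day 10 | 30×10/35 = 8.6 | -1.2 | 5 points |
| 40% from day 8 | 30×8/40 = 6.0 | -1.4 | 10 points |
| 45% from day 10 | 30×10/45 = 6.7 | -2.6 | 15 points |
| 50% from day 10 | 30×10/50 = 6.0 | -3.2 | 20 points |

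The first row shows that the rule works when the bend is at 30%. In the others the knot precedes the bend, and β2 averages the rest of the decline with the flat phase.

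**Step 2: locating the bend with noise, n = 30.** The 30% rule takes the first whole day with mean change at or below -30%. The estimated knot is the least-squares profile over days 2-12. The share of simulated trials with the knot within 2 days of the bend, across the four SD sets, was:

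- 45% from day 10: about 30-35% by the 30% rule, against 70-94% when estimated.
- 35% from day 10: 65-93% against 63-86%, so no gain.
- 30% from day 6: 74-80% against 71-97%, so no clear gain.

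**Step 3: too few days after the knot.** For a straight decline reaching p% on day 13, the crossing is on the first whole day d with p × d / 13 ≥ 30.

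- p = 30 to 32: day 13, leaving 0 later days. Then max(d − 13, 0) = 0 on every day, so neither β2 nor its random effect can be estimated.
- p = 35: day 12, leaving 1 day. The standard error of β2 is 3.1-7.3 points/day at n = 30, against a true slope of 35/13 = 2.7.
- p = 40: day 10, leaving 3 days.

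No knot, or a knot on day 13, occurred in 40-67% of simulated trials for a line ending at 30%, 20-27% for 35% and 2-10% for 40%.

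**The case against.** The strongest reply is that the model asks a different and legitimate question: does pain keep falling beyond the candidate dose? The dose candidate uses the same 30% level, and the SAP never says that the knot estimates where the plateau begins. On that reading β2 is correct. This stands, and it limits how the simulations may be used. A reader might infer that the planned model gives false findings at high rates, since a significant post-knot decline appeared in 58-96% of trials for 45% from day 10 and 18-34% for 35% from day 10, against 2-3% when the plateau is at 30% from day 6. Those are not error rates. Pain really does fall by a further 15 or 5 points after the 30% point in these curves, and the test detects it. The result misleads only if β2 is read as the slope of the plateau. What remains is that the SAP gives the plateau as the model's purpose and β2 does not describe it unless levelling starts at 30%.

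Second, the ANOVA tests for non-linearity without a knot, the daily means are plotted, and graphical checks are planned. These are real safeguards, but partial ones. The ANOVA can show a bend without placing it, and no rule says what happens to the knot if the plots show misfit.

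Third, a pre-specified knot is simple, and estimating one from 30 people is imprecise. That is fair. It is why relabelling the slope is an acceptable minimum.

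A reader might also extend the point to Aim 3, where the rule is repeated at 20%. The SAP gives that model no plateau purpose, so the documents show no error there.

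**Conclusion.** The concern holds in a limited form. Fixing the knot at 30% describes change before and after a clinical threshold. It describes the plateau only if response levels off at that threshold. The discrepancy is minor for a plateau just above 30% and material for higher, later ones. The clearer gap is that the model has no usable second segment if the mean does not reach 30% before day 13, and no fallback is stated.

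The logic rests on the SAP's text alone. The percentages rest on assumed curves, assumed SDs, independent daily errors, complete diaries and the sample-mean reading of the knot. Harm is confined to this exploratory model, and to mood and sleep only if the plan means to carry the 30% knot to them. The ANOVA effect size, its significance and non-linearity tests, and the plotted dose candidate do not use the knot. The model should be corrected before analysis; the trial's other conclusions are not affected.

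**What to change.** **Preferred.** Estimate the Aim 2 change point by profile likelihood over interior treatment days (for example days 2-12), with a subject-level bootstrap 95% interval. Compare this model with a linear mixed model without a bend, using a reference distribution that allows for the knot search, such as a parametric bootstrap. This matters because a plain 5% test at the best-fitting knot called a bend in 19-21% of simulated straight-line trials. Report the day the mean crosses 30% separately as the dose candidate, or state that it was not reached.

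**Minimum.** Keep the 30% knot, label the second slope as change after the 30% point rather than plateau, and specify a no-knot or estimated-knot model if 30% is not reached or is reached only on the last days.

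Either way, say whether the 30% level is the sample mean's, and whether the same model is meant for mood and sleep.

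**Cost.** SAP wording and modest extra analysis; no new data. The downside of the preferred option is precision. Over the 10-day search range at n = 30, the median interval width across the SD sets was 3.5-9.0 days for 30% from day 6 and 6.0-10.0 days for 45% from day 10. The calibrated bend test detected that late bend in 27-93% of trials. Report the interval as it is, however wide, without a fixed cut-off for calling the day undetermined. The change avoids a wrong statement about the plateau but does not guarantee a precise day.

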A sample protocol for this pilot study is shown in the Figure above. On Day 1 (lab visit #1) subjects will complete questionnaires, receive a wrist activity monitor, and a Personal Data Assistant (PDA; electronic diary) to record their daily pain, mood, sleep, and substance use (alcohol, caffeine, prescribed and over the counter medication, heating pads, ice packs, etc) while they sleep ad lib at home, following their usual sleep schedule. They will then undergo pain sensitivity testing (acute pain induction with forearm ischemia and heat, between noon-1pm as per our pilot). On Day 8 (lab visit #2) subjects will complete questionnaires, have their diaries and wrist actigraphy data reviewed and then will undergo pain sensitivity testing again. Following this subjects will be trained in home saliva collection, receive a kit to take home and will complete their saliva collection that night. The following morning (Day 9, home visit #1) two research staff (mixed gender team) will visit the subject in their home to set up and instruct the subjects in the bright light treatment, and collect their saliva kit and samples. Subjects will self-administer the bright light for 1 h/morning for 6 days before returning to the lab (Day 15, lab visit #3) for repeat questionnaires, review of their diaries and wrist actigraphy, pain sensitivity testing and issuing of the saliva collection kit. Research staff will again visit their homes to collect the saliva kit and samples (Day 16, home visit #2). After a further 7 days of bright light treatment, subjects will return for their last lab visit (Day 22, lab visit #4) for questionnaires, review of their diaries and wrist actigraphy, repeat pain sensitivity testing and issuing of the saliva collection kit. The following morning on Day 23 another home visit (home visit #3) will occur, and research staff will collect the light boxes, saliva kit, samples, and wrist monitors. The PDAs for electronic diaries will be left with the subject. During a 1 month follow up after cessation of the bright light treatment, subjects will continue to report their pain, mood and sleep once a day on the electronic diaries (once a day only to reduce burden and improve compliance). At the end of the follow up staff will collect the PDAs with electronic diaries during a final home visit.

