Aim 3. To determine time course of decay of treatment response (decreased pain intensity) after cessation of light treatment. For Aim 3, we will plot daily diary ratings of pain intensity expressed as percentage change from the mean of pain ratings over the last 3 days of bright light treatment. The point where the mean change for the whole sample achieves 20% (less than a “moderate” decrease [137]) will reveal a potential candidate time for a maintenance dose of bright light. Second, we will subject these data to a within-subjects ANOVA to determine: a) effect size of erosion over 4 weeks of follow-up; b) statistical significance of this change. A change point modeling strategy similar to Aim 2 will be used here, but the change point will be set at a 20% level rather than a 30% level. Secondary analyses involving daily diary ratings of sleep and mood will be conducted as described above. Hypothesis 1: A mean increase of 20% in pain ratings is expected to occur within the first week post treatment (as per winter depression studies [125, 126, 131]). Hypothesis 2: Pain intensity is expected to return to baseline by 1 month post treatment (as per winter depression studies [125, 126, 131]).

We will also examine effects of other factors on treatment response. We will determine whether analyses must be adjusted for confounding factors including but not limited to age, BMI, race/ethnicity, employment, physical workload, any comorbidity (including depression and anxiety), history of traumatic brain injury, time from onset of chronic pain, current psychotropic and analgesic medications, and other treatments being received for chronic pain and/or PTSD. These analyses may involve treating these factors as time-varying covariates. We will also determine whether key factors moderate treatment response. We plan to test whether men or women

and those with low vs. high psychiatric symptoms (e.g., PTSD) show evidence of differential treatment response. These analyses will involve testing Sex or Psychiatric Symptom x Time interactions on pain intensity during and following treatment. In other exploratory analyses we will examine the correlations between change in DLMO and DLMO to midpoint of sleep interval and change in pain, mood and sleep.

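### Daily mood and sleep ratings appear to inherit pain's percentage-change rule, so the 30% and 20% points and the knots placed at them depend on which end of the scale is zero

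*SAP*

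**What the plan says.** In the SAP, Data Analysis, Aim 2, daily pain is plotted as "daily diary ratings of pain intensity expressed as percentage change from baseline pain intensity (mean intensity over the 7 days of baseline" period. A candidate dose is then read off: "The point where the mean change for the whole sample achieves 30" per cent. The 30% figure is supported by a citation to a clinically meaningful effect and is introduced for pain intensity. A within-subjects ANOVA follows, and then, to study a plateau, "we will use a piecewise linear mixed model with a fixed change point occurring at the 30% change level". After the model description comes the sentence on the other diary items: "Secondary analyses for daily ratings of mood and sleep will be conducted similarly".

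The PTSD, depression, anxiety and sleep questionnaires get a separate plan in the next sentence: within-subjects ANOVAs, with no percentage and no change point.

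Aim 3 repeats the pattern for the follow-up month. Pain is "expressed as percentage change from the mean of pain ratings over the last 3 days of bright light treatment", and "the change point will be set at a 20% level rather than a 30% level". Then: "Secondary analyses involving daily diary ratings of sleep and mood will be conducted as described above".

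The Protocol says only that subjects use the diary "to record their daily pain, mood, sleep, and substance use". Neither document gives a range, anchors, scoring direction, separate derivation or separate threshold for the mood or sleep items.

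**The concern.** Percentage change is meaningful when zero means absence of the thing measured. Pain intensity is conventionally scored that way, and the plan cites a benchmark for it. A bounded mood or sleep rating can be scored with either the good or the bad end at zero. Reversing it leaves the change in points the same apart from sign, but it changes the denominator and therefore the percentage.

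Three results follow from that percentage: whether the sample reaches 30% or 20%, on which day it does, and where the knot of the piecewise model sits. If the pain method is carried over, all three reflect a coding choice as well as the light treatment. Improved mood and sleep are named secondary outcomes under Aim 2, so these time-course results are likely to be reported.

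**Working it through.** **Inputs from the documents.** Reference means: 7 baseline days (Aim 2) and the last 3 treatment days (Aim 3). Levels: 30% and 20%. Treatment length: 13 days. Sample: n = 30. The plan states no figure of its own on this point, so there is nothing to reproduce first.

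**Assumptions.** A 0-10 item, because no scale is given. Let b be the reference score with high = bad, and d the improvement in points.

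**Formulas.** With high = bad, percentage improvement = 100 × d / b. With the same item scored high = good, the reference score is 10 − b and percentage improvement = 100 × d / (10 − b).

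**One-point improvement (d = 1):**

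| b (high = bad) | high = bad | high = good |
|---|---|---|
| 2 | 1/2 = 50.0% | 1/8 = 12.5% |
| 3 | 1/3 = 33.3% | 1/7 = 14.3% |
| 4 | 1/4 = 25.0% | 1/6 = 16.7% |
| 5 | 1/5 = 20.0% | 1/5 = 20.0% |
| 7 | 1/7 = 14.3% | 1/3 = 33.3% |

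At b = 3 the two codings fall on opposite sides of 30%. Reaching 30% takes 0.3 × 3 = 0.9 points on one coding and 0.3 × 7 = 2.1 on the other. At the midpoint they agree.

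**Other ranges.** With the reference 30% of the range from the good end and an improvement of 10% of the range (high = bad / high = good): 0-100, 33.3% / 14.3%; 1-10, 24.3% / 12.3%; 1-7, 21.4% / 11.5%; 1-5, 18.2% / 10.5%. The gap persists, but on the last three both values are below 30%.

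**Crossing day.** For a steady 2-point improvement over 13 days from b = 3, the slope is 2/13 points per day. With high = bad, 30% is reached on day 0.9 / (2/13) = 5.85. With high = good it is 2.1 / (2/13) = 13.65, after treatment has ended.

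**Aim 3.** One point of worsening from an end-of-treatment score of 2 (high = bad) is 1/2 = 50%. On the reversed item it is 8 to 7, or 1/8 = 12.5%. These lie on opposite sides of 20%.

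**Simulation.** Assumed: n = 30, between-subject SD 1.5, daily SD 1.0, linear gain over 13 days, ratings clipped to 0-10, percentage taken from the sample means. Each trial is scored both ways. The table shows the share of trials in which some daily mean reaches 30%:

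| Baseline (high = good), gain by day 13 | high = good | reversed |
|---|---|---|
| 7, 1 point | 0% | 76% |
| 6, 1.5 points | 7% | 98% |
| 6, 1 point | 0% | 19% |
| 5, 1.5 points | 60% | 63% |
| 5, 2 points | over 99% | over 99% |
| 6 or 7, 0.5 points | 0% | at most about 2% |

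Counting any of 13 days favours crossing. On day 13 alone, the 76% falls to about 51%, still against 0%.

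**Point change.** Reversing the scale turns d into −d and nothing else. In one illustrative data set (n = 30), the day-13 paired t on raw change was 11.42 on both codings. On percentage change it was 11.01 (high = bad) and 10.03 (high = good).

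**The case against.** The strongest reply is about the text. Neither cross-reference repeats percentage change, 30% or 20% for mood or sleep, and the Aim 2 sentence closes a run of modelling steps, so it could mean only the ANOVA and mixed-model sequence. The candidate-dose decisions are also tied to pain. This stands as a caution: the application to mood and sleep is an inference. It remains the natural reading, because no other derivation for daily ratings is given, a knot at a 30% or 20% change level needs a percentage, and the questionnaires are explicitly given a plan without one. On the looser reading, the mood and sleep derivation is simply unspecified and the same sentences need rewriting.

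Second, the scale facts are assumed. An item scored as symptom intensity would have a zero like pain's, and sleep recorded as a duration has a natural zero. That stands, although the SAP calls these items ratings.

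Third, the consequence is limited. These are secondary analyses in a 30-person pilot with no decision rule for mood or sleep. ANOVA on raw ratings does not depend on direction, and even on percentages the illustrative t statistics differed little. That also stands.

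Two stronger inferences are tempting and not supported. A reader might infer that the Aim 3 event points the wrong way for a higher-is-better item, because a 20% increase is hypothesised. That hypothesis concerns pain ratings only; the 20% method sentence speaks of change without a direction. A reader might also infer that mood and sleep are uniquely exposed to a missing knot if the level is never reached. The same is true of pain, so it is not part of this point.

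**Conclusion.** The concern holds in a limited form. Followed as naturally read, the plan makes the percentage, the crossing day and the knot for daily mood and sleep depend on scoring direction. How much depends on the unstated scale, the baseline and the gain. On an assumed 0-10 item it can decide the result (0% versus 76% of simulated trials reaching 30% at baseline 7 with a 1-point gain), or make almost no difference near the midpoint or with a 0.5-point gain. The 14% and 33% figures are illustrations, not values from the documents.

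It would be wrong to infer that the pain results, or every test of whether mood and sleep improve, are compromised. The effect is confined to the secondary threshold, crossing-day and change-point results. The wording should be changed, because the rule as read gives a coding-dependent answer and a better method uses the same data.

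**What to change.** In the SAP, Data Analysis, replace the cross-references for daily mood and sleep in Aims 2 and 3. State that these ratings are analysed in scale points, as change from each subject's 7-day baseline mean (Aim 2) and last-3-day treatment mean (Aim 3), in a linear mixed model over days. Report the mean change with a 95% CI, and a standardised effect such as the change divided by the baseline SD. State each item's range, anchors and direction.

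Do not apply the 30% and 20% levels, or knots placed at them, to mood and sleep; keep them for pain intensity. Keep the planned ANOVA test of non-linearity in Aim 2 to assess a plateau.

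The cost is a few sentences, with the same data and software. The loss is a percentage figure for mood and sleep to set beside pain.

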Bright Light Treatment At Home To Manage Chronic Pain In U.S. Veterans

NCT02373189

Document Date: 12/23/22

Data Analysis

Aim 1. To determine the feasibility and acceptability of bright light treatment in a sample of US veterans (n=30) experiencing chronic low back pain. For Aim 1 we will track the number of US veterans who express interest in the study, the number that meet our inclusion criteria, the number that enroll, the number of mornings that bright light is self-administered and the duration of the exposure, and we will collect treatment expectancy and treatment satisfaction ratings. Hypothesis 1: We expect reasonable feasibility in that (i) we will be able to enroll 2 US veterans per month, (ii) $\geq 75\%$ of those enrolled self-administer at least 30 mins of morning bright light on at least 50% of treatment days (this light should still be somewhat effective, as per winter depression studies [125, 126, 131]). Research Strategy Page 54 Contact PD/PI: [name] Hypothesis 2: We expect reasonable acceptability in that (i) at least 1 in 4 US veterans who are eligible for the study agree to participate, (ii) average expectancy rating at start of bright light treatment is $\geq 6/10$, (iii) the attrition rate is $\leq 30\%$, and (iv) average treatment satisfaction at end of bright light treatment is $\geq 6/10$. Aim 2. To examine the effects of 6 days and 13 days of bright light treatment on chronic pain intensity and sensitivity in US veterans (improved PTSD symptoms, mood and sleep are secondary outcomes).

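### For the lab-visit questionnaires the SAP names only within-subjects ANOVA and gives no missing-data rule; a repeated-measures mixed model would cheaply keep visits that the classical ANOVA drops

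*SAP*

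**What the plan says.** The Protocol puts questionnaires and pain testing at four lab visits. At the first, "On Day 1 (lab visit #1) subjects will complete questionnaires" and are then tested for pain sensitivity. Day 8 repeats both at the end of baseline. Day 15, after 6 days of light, calls for "repeat questionnaires, review of their diaries and wrist actigraphy, pain sensitivity testing". Day 22, after 13 days of light, does so again.

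The SAP (Data Analysis, Aim 2) assigns these methods:

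- **Questionnaires:** "For additional secondary analyses involving PTSD, depressive and anxiety symptoms, and sleep questionnaires, we will subject data to within-subjects ANOVAs to determine" effect sizes, significance and any plateau. No other model is named for them.
- **Heat and ischemia sensitivity:** "We will also examine pain sensitivity (ischemia, heat) changes over the 4 lab visits". After Hypothesis 3, which covers both pain intensity and sensitivity, comes "As a preliminary analysis, we will examine these data with a within-subjects ANOVA to determine" the same three things.
- **Plateau:** "we will use a piecewise linear mixed model with a fixed change point occurring at the 30% change level", with random effects for time before and after that point. The SAP then says that daily mood and sleep ratings are handled in a similar way, before it turns to the questionnaires.

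Aim 1 plans the study "in a sample of US veterans (n=30) experiencing chronic low back pain". Hypothesis 2 there counts attrition of no more than 30% as acceptable. Neither document defines the attrition period, an analysis set, an imputation method or any rule for a missed visit.

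**The concern.** A classical within-subjects ANOVA over visits needs a complete row for each subject. A veteran who attends Days 1, 8 and 15 and then leaves contributes nothing, although three of the four measurements are in hand. A subject who sees no benefit by Day 15 has a plausible reason to leave. If such subjects do leave, the analysis of those who stay overstates improvement and rejects too often. With no control group, nothing in the design would reveal this. Effect sizes are a stated output of these analyses, and sensitivity carries a 30% criterion in Hypothesis 3(ii). The Day 15 values that could correct the selection are collected but unused.

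**Working it through.** The documents give no power, alpha, SD or sample-size derivation, so there is no planned figure to reproduce.

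**Inputs from the documents.** n = 30 and an attrition ceiling of 30% (SAP, Aim 1); visits on Days 1, 8, 15 and 22 (Protocol).

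**Assumptions.** SD 1 at each visit; equal correlation rho = 0.7 between visits (0.5 to 0.8 also tried); negative change means improvement; all leavers go between Day 15 and Day 22; two-sided 5% test.

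**1. Subjects and records lost.** 30 x 0.30 = 9 leavers at the ceiling, so 21 remain. If all leave after Day 15, 9 x 3 = 27 completed visit records per outcome go unused. If all leave after Day 8, 9 x 2 = 18 do.

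**2. Bias by formula.**

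- The Day 8 to Day 15 change has variance 2(1 - rho) = 0.6, so SD 0.775.
- Its covariance with the Day 8 to Day 22 change is 1 - rho = 0.3, so the regression slope is 0.3/0.6 = 0.5.
- If the worst fraction f at Day 15 leaves, the mean standardised Day 15 change of those who stay shifts by -phi(z)/(1 - f), where z is the upper f point of the normal distribution.
- 9 worst leave (f = 0.30): z = 0.524, phi = 0.348, shift = -0.348/0.70 = -0.497. Bias = 0.5 x 0.775 x (-0.497) = -0.19 SD.
- 3 worst leave (f = 0.10): z = 1.282, phi = 0.1755, shift = -0.1755/0.90 = -0.195. Bias = 0.5 x 0.775 x (-0.195) = -0.076 SD.
- If leaving depends on the Day 15 change plus independent noise of the same SD, multiply by 1/sqrt(2) = 0.707. This gives about -0.05 SD for 3 leavers and -0.19 x 0.707 = -0.13 SD for 9.

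**3. Simulation** (4,000 trials per row, rho = 0.7, no true change):

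| Dropout after Day 15 | Complete-case Day 22 minus Day 8 | Rejection at nominal 5% |
|---|---|---|
| 9 at random | 0.00 SD | about 5% |
| 3, partly related to response | -0.05 SD | about 6% |
| 3 worst responders | -0.07 SD | about 9% |
| 5 worst responders | -0.11 SD | about 12% |
| 9, partly related to response | -0.13 SD | about 12% |
| 9 worst responders | -0.19 SD | about 21% |

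A likelihood estimate using all visits is unbiased (0.00 SD) in all these settings. With a true change of -0.50 SD and the 9 worst leaving, completers give -0.69 SD and the likelihood estimate -0.50 SD. At rho 0.5 and 0.8 the complete-case figures are -0.73 and -0.65 SD.

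**4. Limits of the alternative.** If leaving depends on the unobserved Day 22 state (9 leavers, no true change), the likelihood estimate is itself biased by about -0.30 SD, against -0.37 SD for completers. Under random dropout it gains little precision (standard error 0.164 vs 0.170 SD).

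**The case against.** Four objections have weight.

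- **Exclusion is not stated.** A reader might infer that the plan says it will discard incomplete subjects. It does not. The loss follows from the classical form of the named method together with silence on missing data.
- **Sensitivity may already be covered.** A reader might infer that every lab-visit outcome stays with ANOVA and that the mixed model is for diary data only. The SAP does not say so: the sensitivity ANOVA is called preliminary, and the piecewise model that follows is not restricted to diary ratings. This stands as an ambiguity. Even so, that model addresses the plateau, its change point is the 30% level that the SAP reads from the daily diary plot, and there are only two on-treatment visits to support slopes before and after it. It is a poor vehicle for the Day 22 minus Day 8 change in sensitivity. The ambiguity does not extend to the questionnaires.
- **The largest figure is an extreme case.** A reader might infer that 9 subjects will be lost before Day 22 and that a false-positive rate near 21% is to be expected. The 30% is an acceptability ceiling, not a forecast, and its period may include the 1-month follow-up, when all four lab-visit measurements are complete. Nothing in the documents supports exact dropout of the worst responders.
- **A mixed model is not a cure.** It corrects dropout that depends on observed values only, as step 4 of the working shows.

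It also stands that this is an uncontrolled pilot, that the questionnaires are secondary, and that no decision rule rests on their significance.

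**Conclusion.** The point holds as a cheap improvement. It is firm for the PTSD, depression, anxiety and sleep questionnaires, where ANOVA is the only named method and no missing-data rule exists. It applies also to the preliminary ANOVA of heat and ischemia sensitivity, with the reservation that a mixed model may be meant to follow there. The overstatement of the Day 8 to Day 22 change is between about -0.05 and -0.19 SD for 3 to 9 response-related leavers, with rejection of 6% to about 21% under no true change, and none if dropout is random. These figures rest on an assumed correlation of 0.7, an assumed dropout mechanism, and all leavers going between Days 15 and 22. Only the sample size, the visit days and the 30% ceiling come from the documents.

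**What to change.** Replace the within-subjects ANOVA for the questionnaires and for heat and ischemia sensitivity with a linear mixed model for repeated measures:

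- Visit (Days 1, 8, 15, 22) as a category, unstructured covariance, REML and Kenward-Roger degrees of freedom. Four visits mean 4 x 5/2 = 10 covariance parameters from at most 30 subjects, so name a simpler covariance as fallback.
- Include every subject with at least one visit.
- Report the Day 15 minus Day 8 and Day 22 minus Day 8 contrasts with 95% CIs. Take the effect size and the non-linearity contrast from the same model.
- State that the model assumes dropout depends only on observed values.
- Add one sensitivity analysis, for both the questionnaires and pain sensitivity, that scores subjects without Day 22 as unchanged from Day 8. This pulls the estimate towards zero but does not remove bias: with 9 leavers it is 21/30 of the complete-case mean, so -0.19 becomes 0.7 x (-0.19) = -0.13 SD. Use it to see whether an effect survives, not as a corrected estimate.

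The cost is SAP wording and a little more analysis; the SAP already uses mixed models. Under response-related dropout the Day 22 standard error is somewhat larger (about 0.20 vs 0.17 SD in the simulation with 9 leavers), which reflects the missing information.
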